### Power analysis

With a total of N=540 after attrition, the expected 95% confidence intervals are (7.7%, 12.8%) and (3.5% and 7.2%) for the resistance and reinfection rates, respectively. For the bivariate analysis, any binary variable with odds-ratio (OR)  $\geq 1.8$  (or 7% vs. 14.4%) for resistance and OR  $> 3.3$  (or 2.5% vs. 7.8%) for reinfection will be identified with >80% power; and any continuous variable with OR $>1.6$  and OR $>2.1$  per 1 SD unit changes will be detected for resistance and reinfection, respectively. In the multivariable analysis, binary variables with OR  $> 2.5$  (7% vs. 16.2%) and OR  $> 4.0$  (2.5% vs. 9.3%) and continuous variables with OR 1.8 and OR $>2.5$  per 1 SD unit change will be detected for resistance and reinfection, respectively, with >80% power, expecting that as large as 30% of variation of each variable will be explained by the other variables in the models for aim 2 analyses. Likewise, for detecting association between a continuous

adherence rate and resistance, OR  $\geq 1.8$  per 1 SD unit change will be detected with  $> 80\%$  power.

## 11.12 Analytic plan for Aim 3

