**Figure 1: Schematic of Study Design**

## PROTOCOL SUMMARY

Title:	Patient-Centered Models of HCV Care for People Who Inject Drugs
Design:	Two arm study evaluating modified directly observed therapy (mDOT) versus patient navigator (PN) to deliver HCV treatment to PWID in two health settings: (1) opioid treatment program (OTP), (2) community health center (CHC) -Sites in eight cities (16 programs)
	Total number of subjects: Up to 1000 subjects will be enrolled and randomized with an expected 600 participants initiating treatment.
	Participants: 600 subjects on treatment Arm A: (1) OTP, N=150; (2) CHC, N=150 Arm B: (1) OTP, N=150; (2) CHC, N=150
Population:	Adults of any gender with current Hepatitis C Virus (HCV) infection, people with recent active injection drug use, 18 – 70 years old.
Number of Sites:	Eight Sites (Montefiore Medical Center, New York; West Virginia University, Morgantown; University of Washington, Seattle; University of Rhode Island, Providence; University of California San Francisco; The Johns Hopkins University, Baltimore; University of New Mexico, Albuquerque)
Study Duration:	Approximately 6 years
Subject Participation Duration:	Up to 180 weeks: up to 12 weeks of pre-treatment evaluation, 12 weeks of treatment, 12 weeks of follow-up to determine Sustained Virologic Response (SVR) 12, and 144 weeks of follow-up to determine long-term SVR and reinfection
Description of Intervention:	Participants will be randomized to one of two treatment

model arms: A: mDOT or B: PN, at one of two clinical sites: 1) opioid treatment program (OTP) or (2) community health center (CHC) setting.

Objectives:

1. To determine whether SVR-12 rates are higher among those randomized to mDOT compared to those randomized to PN, among People Who Inject Drugs (PWID) treated at opioid treatment program (OTP) and community health centers (CHC).
2. We will also examine the following outcomes overall, and by randomization arm (mDOT vs. PN):
  - (1) HCV treatment initiation
  - (2) Adherence
  - (3) Treatment completion
  - (4) Drug resistance
  - (5) HCV reinfection
3. To examine factors associated with key study outcomes (treatment initiation, adherence, SVR, drug resistance and HCV reinfection) using quantitative and qualitative methods.

Estimated Date of Completion:

2022

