### 3 Study Objectives

#### 3.1 Primary Objective

To determine whether SVR-12 rates are higher among those randomized to mDOT compared to those randomized to PN, among PWID treated for HCV at OTPs and community health centers.

#### 3.2 Secondary Objective 1

To examine the following outcomes overall and by randomization arm (mDOT compared to PN) among PWID treated at OTPs and community health centers:

- (i) Treatment initiation: whether a higher proportion of participants in the PN arm initiate treatment compared to mDOT arm;
- (ii) Adherence ( $\geq 80\%$  of prescribed medication taken): whether a higher proportion of those in the mDOT arm are adherent compared to PN arm;
- (iii) Treatment completion (finishing 100% of prescribed 12-week course): whether a higher proportion of participants in the mDOT arm complete treatment compared to PN arm;
- (iv) Drug resistance: whether the proportion who develop drug resistance is higher in the PN arm compared to mDOT arm;
- (v) Reinfection: whether (a) rate (incidence), and the (b) proportion who become reinfected with HCV is higher in the PN arm compared to mDOT arm;

Comparisons will be performed to determine the proportion of subjects in each arm who: a) initiate treatment; b) adhere to antiviral treatment; c) complete antiviral treatment; d) attain SVR (cure); e) develop drug resistance; f) reinfection. We will also conduct time to event analyses to examine drug resistance and reinfection outcomes. Subgroup analyses will be performed to assess differences in outcomes among those randomized to PN vs. mDOT in specific sub-populations.

#### 3.3 Secondary Objective 2

To examine factors associated with key study outcomes (treatment initiation, adherence, SVR, drug resistance and HCV reinfection) using quantitative and qualitative methods.

Quantitative methods: We will examine associations between psychosocial factors such as homelessness, co-morbid mental illness, poor social support, and high

levels of shame and stigma, with key study outcomes described above. It is hypothesized that these psychosocial variables are associated with lower rates of adherence and SVR in the PN arm, but not the mDOT arm; and associated with lower rates of treatment initiation in the mDOT arm, but not the PN arm.

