### 11.2 Definition of Study Subjects

The study subjects for the primary and secondary outcomes are who: 1) meet the inclusion and exclusion criteria (sections 5.1 and 5.2); 2) sign the consent form; 3) are randomized; and 4) initiate treatments, i.e., intake at least one dose of the medicine. As we do not anticipate that all randomized subjects will initiate treatments, a randomized subject will not necessarily be a study subject for primary analysis and beyond. However, depending on secondary or other study questions such as comparison of treatment initiations, all randomized subjects will serve as an analytic sample.

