## 11.4 Sample Size Determination

Sample size N=300 per arm, or a total of N=600, was determined based on feasibility of recruitment from all sites during the study period. Power analysis for each hypothesis below is conservatively conducted based on a reduced sample size (N= 270 per arm, or N=540 in total) after considering 10% attrition rates. The target power is 80% with a two-sided significance level of 0.05. To this end, minimally detectable effect sizes and widths of 95% confidence intervals were computed with those parameters and the sample size after attrition.

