## 11.7 Missing data analysis

In order to not compromise internal or external validity of our study results, every effort will be made to minimize missing data that could occur due to missed visits or subject attrition. A maximum 10% subject attrition rate is anticipated during the first 24-week intervention period considering a real-world situation that withstands a tight control. However, the missing outcome data rates will depend on the outcome definition whereas most analyses will use baseline characteristics as covariates that will thus have negligible missing data rate.

The primary analysis will be based on available data without missing data imputation; however, we will conduct variety of missing data imputation methods for sensitivity analyses. Depending on the clinical nature of outcome, worst scenario imputation or, if deemed more relevant, mean imputation methods will be considered. In addition, fully specific conditional specification multiple imputation methods will also be applied, which are applicable to non-ignorable missing data.

Characteristics of patients who are lost to follow-up will be compared to those that remain in the study to assess the degree of any selection bias due to attrition, and the analysis results of the different types of imputed missing data will be compared to the primary analysis results. In particular, variability of the coefficients of primary predictors across the different imputation methods will be assessed to evaluate robustness of the findings. If the changes in the coefficients are greater than 15% from those of the primary analysis, we will limit the generalizability, internal and external validity of our findings, which we nevertheless do not believe will occur if attrition rates are less than 25%.

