## 11.11 Analytic plan for Resistance and Reinfection Rates

### Study Hypotheses:

**Detectable resistance:** Patients in the PN arm will have higher resistance rate, compared to the mDOT arm. We hypothesize that the majority (65%) of patients who fail to achieve SVR will develop detectable resistance, yielding an overall 10% resistance rate.

**Reinfection rate:** The hypothesis is that there will be a minimum 5% reinfection rate based on meta-analysis of reinfection rates in patients treated with IFN-based regimens.

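### Protocol 11.11 sizes the reinfection analysis on all 540 retained initiators, although the protocol's own assumptions leave only about 457 who could be reinfected

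*Protocol*

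**What the plan says.** Protocol 11.2 defines the study subjects for primary and secondary outcomes as eligible, consented, randomised participants who "initiate treatments, i.e., intake at least one dose of the medicine". It allows a different sample for some secondary questions, but the one it names is wider (all randomised), not narrower.

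Reinfection is secondary outcome (v) in Protocol 3.2. It has two parts: incidence, and whether the "proportion who become reinfected with HCV is higher in the PN arm compared to mDOT arm". Section 3.2 also promises time-to-event analyses of reinfection.

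Section 11.11 analyses the proportion of participants reinfected, with exact binomial intervals and logistic models for associated factors. Its power paragraph reads: "With a total of N=540 after attrition, the expected 95% confidence intervals are (7.7%, 12.8%) and (3.5% and 7.2%) for the resistance and reinfection rates". It then claims more than 80% power for 2.5% vs 7.8% (OR 3.3) in bivariate analysis and for 2.5% vs 9.3% (OR 4.0) in multivariable analysis with 30% explained variation. Section 11.4 says that power is "based on a reduced sample size (N= 270 per arm, or N=540 in total) after considering 10% attrition rates".

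The same section 11.11 assumes that "the majority (65%) of patients who fail to achieve SVR will develop detectable resistance, yielding an overall 10% resistance rate". The SAP defines only ITT, mITT and per-protocol samples and has no reinfection analysis.

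**The concern.** Reinfection presupposes clearance. An initiator who never clears the virus can contribute a zero to the reinfection count but can never contribute an event. If such people sit in the planning N, precision and power are computed on more people than can inform the rate.

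If they also sit in the analysis denominator, the reinfected proportion becomes the product of two things: the chance of clearing and the chance of reinfection after clearing. The trial is designed to detect a difference between arms in the first of these, so a comparison of the product mixes the two. The same applies to the factor models in 11.11: a characteristic that lowers SVR would also lower apparent reinfection.

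**Working it through.** **Inputs.** Two-sided 0.05 and 80% target power (11.4). N = 600 × 0.9 = 540, or 270 per group (11.4). Reinfection 5% (11.3, 11.11). Stated effects and 30% explained variation (11.11). Resistance 10% overall, from 65% of SVR failures (11.11). SVR 80% in PN, and 89% as the detectable mDOT value (11.10).

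**1. The plan's own figures.** With n per group and p̄ the mean of the two rates, power = Φ{[|p1 − p2|√n − 1.96√(2p̄(1 − p̄))] / √(p1(1 − p1) + p2(1 − p2))}.

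- Bivariate, n = 270, 2.5% vs 7.8%: (0.8709 − 0.6126)/0.3103 = 0.832, so power is 79.7%.
- Multivariable, n = 270 × 0.7 = 189, 2.5% vs 9.3%: (0.9348 − 0.6531)/0.3297 = 0.854, so power is 80.4%.
- 95% interval for 5% at N = 540: Wilson 3.46% to 7.18%, which matches the stated 3.5% to 7.2%. The exact method named in 11.11 gives 3.32% to 7.19%, an immaterial difference.

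So the stated figures come from all 540, with nothing taken off for non-clearance.

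**2. Number at risk.**

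- From 11.11: SVR failure = 0.10/0.65 = 15.4%; 540 × (1 − 0.154) = 457.
- From 11.10: 270 × 0.80 + 270 × 0.89 = 216 + 240.3 = 456.
- Range: 540 × 0.80 = 432 to 540 × 0.89 = 481.

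**3. Figures at the number at risk, taking the stated rates as rates among those at risk.**

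| N at risk | Power, 2.5% vs 7.8% | Power, 2.5% vs 9.3%, 30% explained |
|---|---|---|
| 540 (as planned) | 79.7% | 80.4% |
| 481 | 75.0% | 75.6% |
| 457 | 72.8% | 73.5% |
| 432 | 70.4% | 71.1% |

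At 457, 80% power is reached at about 2.5% vs 8.5% (OR 3.6) and 2.5% vs 10.1% (OR 4.4). The exact 95% interval for 5% is 3.2% to 7.4%.

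Keeping all 540 in the denominator does not recover the power. Multiplying the rates by the mean SVR of 0.845 gives about 2.1% vs 6.6%, with power 72.4%.

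**4. By-arm proportion.** With risk r after clearance equal in both arms, the reinfected share of initiators is 0.80r in PN and 0.89r in mDOT. The ratio mDOT/PN is 0.89/0.80 = 1.11 for any r. At r = 5% this is 4.00% vs 4.45%. Equivalently, a true PN/mDOT ratio is multiplied by 0.80/0.89 = 0.90. With equal SVR the factor is 1. The 0.45-point shift compares with a standard error of √(0.04 × 0.96/270 + 0.0445 × 0.9555/270) = 1.7 points.

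**The case against.** **The documents never say that people who did not clear are analysed for reinfection.** That is correct. A reader might infer from 11.2 that they certainly will be, but 11.2 is a generic definition and 540 is a planning number shared with resistance. Protocol 2.1 and section 8 frame reinfection testing and follow-up as starting after SVR12. These passages set a visit schedule, however, not an analysis set, and nothing in either document narrows the denominator. What stands is that the risk set is undefined and the planning N was not reduced.

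**Incidence and time-to-event analyses are also planned.** They avoid the denominator problem if person-time starts at clearance, but no time origin is given. The proportion in 3.2(v)(b) and the logistic models in 11.11 remain exposed. A reader might conclude that a by-arm bias is built into the reinfection objective. The documents do not support that: the distortion needs unequal SVR, 89% is a detectable value rather than a forecast, and at 5% reinfection the shift is about a quarter of a standard error.

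**The stated rates may be proportions of initiators.** Then 79.7% stands for that quantity, and only the interpretation problem remains. The protocol does not say which is meant.

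**Five percent is a stated minimum.** Section 2.1 cites 3.2 to 5.2 per 100 person-years. At a constant rate with complete follow-up, 1 − exp(−0.032 × 144/52) = 8.5% and 1 − exp(−0.052 × 144/52) = 13.4% over the 144 weeks after SVR12. With two equal groups averaging those risks at OR 3.3 (4.2% vs 12.8%; 7.0% vs 19.8%), power at 457 is about 91% to 98%. The event rate therefore matters more than the denominator. Working the other way, the 10% loss is qualified in 11.7: "A maximum 10% subject attrition rate is anticipated during the first 24-week intervention period". Visits run to week 168, and the last four required fresh consent.

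**Conclusion.** The point holds as a planning error of moderate size together with an undefined risk set. At the plan's own 5% rate and SVR assumptions, about 83 of the 540 are not at risk. The claimed power of more than 80% becomes about 73% (70% to 75% bivariate) if the stated rates refer to people at risk. The figure of 457 is itself a ceiling, because loss after week 24 is not taken off. It does treat every SVR failure as never cleared, so a participant who cleared and was reinfected before the SVR assessment would be miscounted; the plan gives no figure for these.

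The by-arm effect is conditional. It is an 11% relative shift toward the arm with higher SVR at 89% vs 80%, and zero at equal SVR. If SVR is higher in mDOT, as the primary hypothesis expects, the shift runs against the stated expectation of more reinfection in PN.

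**What to change.** In Protocol 11.2 and 11.11, and in the SAP if reinfection is added there:

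1. Define the reinfection risk set as participants with documented clearance and at least one later HCV RNA result. Clearance means SVR by the SAP 5.2 algorithm, including its secondary window to 365 days, plus any earlier clearance followed by sequencing-confirmed reinfection. Excluding every SVR failure would discard those early reinfections.
2. Start person-time at clearance for the incidence and time-to-event analyses.
3. State whether the 5%, 2.5%, 7.8% and 9.3% are rates among those at risk. If so, restate the figures at no more than about 457: exact interval 3.2% to 7.4%, and detectable odds ratios of about 3.6 (bivariate) and 4.4 (multivariable). Note that attrition after week 24 lowers the number further.
4. Label the by-arm comparison among cleared participants as non-randomised, since it conditions on a post-randomisation outcome. Report the whole-arm proportion alongside it, with its denominator stated.

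The cost is wording and slightly less favourable stated figures. HCV RNA is already collected at visits 5 to 17, so no new data or participants are needed.

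### Protocol 11.11 gives a detectable odds ratio of 1.8 for binary factors and resistance, but its own rate pair (7% vs 14.4%) is an odds ratio of 2.23; 1.8 from a 7% base has about 50% power, not over 80%

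*Protocol*

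**What the plan says.** Protocol 11.4 sets the basis for all the power statements: "N= 270 per arm, or N=540 in total) after considering 10% attrition rates", and "The target power is 80% with a two-sided significance level of 0.05".

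Protocol 11.11 (Power analysis) then covers resistance and reinfection. It opens "With a total of N=540 after attrition". For the bivariate analysis it says that "any binary variable with odds-ratio (OR") of at least 1.8, "or 7% vs. 14.4%) for resistance and OR" above 3.3 for reinfection, "will be identified with >80% power". Continuous variables have their own thresholds in the same sentence. The next sentence gives thresholds for the multivariable analysis, allowing for 30% of a variable's variation being explained by the others.

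The resistance rate behind this comes from the hypotheses of the same section: "the majority (65%) of patients who fail to achieve SVR will develop detectable resistance, yielding an overall 10% resistance rate".

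The SAP covers SVR, treatment initiation, completion and adherence. It has no section or power statement on resistance.

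**The concern.** One parenthesis offers an odds ratio and a pair of rates as the same detectable effect. They can be checked against each other by hand, and they disagree. One of them must be wrong, and the stated power can hold for only one of them.

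At stake is how sensitive the factor search for resistance really is. Under the statistical model of 11.11, only factors significant at 0.05 in the bivariate step go on to the multivariable model. A reader who takes 1.8 at face value would think that a binary factor of that strength is unlikely to be missed. If the true threshold is about 2.2, a factor at 1.8 is missed about half the time.

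**Working it through.** **Inputs.** N=540, taken as 270 per group; two-sided 0.05; target power 80% (11.4). Rate pairs and odds ratios from 11.11. The split of a general binary factor is not stated. An even split is assumed because it reproduces the protocol's own 80%.

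**Formulas.** OR = [p2/(1−p2)] / [p1/(1−p1)]. Power = Φ[(|p2−p1| − 1.96·s0)/s1], with s0 = √(2·p̄(1−p̄)/n), s1 = √([p1(1−p1)+p2(1−p2)]/n) and p̄ the mean of the two rates.

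**1. Reproduce the plan's power from the rate pair.** For 7% vs 14.4% and n=270, p̄ = 0.107, s0 = 0.02660 and s1 = 0.02641. Then (0.074 − 1.96×0.02660)/0.02641 = 0.83, and Φ(0.83) = 79.6%. The pair gives the target power.

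**2. Odds ratio of that pair.** (0.144/0.856)/(0.07/0.93) = 0.16822/0.07527 = **2.23**. The risk ratio is 0.144/0.07 = 2.06, so reading 1.8 as a risk ratio does not help.

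**3. Power at the printed odds ratio.** Odds 1.8 × 0.07527 = 0.13548, so p2 = 0.13548/1.13548 = 11.9%. Then s0 = 0.02520, s1 = 0.02511, and (0.0493 − 1.96×0.02520)/0.02511 ≈ 0, so power is **49.9%**.

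**4. Odds ratio needed for 80% power from a 7% base.** About 2.24. At exactly 2.2 the power is 77.8%.

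**5. Can another convention rescue 1.8?**

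| Variant, OR 1.8 | Power |
|---|---|
| Wald test on log OR, 7% base | 49.1% |
| Fisher exact, 7% base | 44.7% |
| One-sided 0.05, 7% base | 62.3% |
| 300 per group, 7% base | 54.1% |
| Overall rate fixed at 10%, split 50:50 | 51.9% |
| Overall rate 10%, 40% exposed | 53.9% |
| Overall rate 10%, 30% exposed | 52.4% |
| Overall rate 10%, 20% exposed | 46.5% |

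None comes near 80%. With an even split, OR 1.8 has 76.2% power from a 15% base and 83.9% from a 20% base. It would need a base rate well above the plan's 10% overall.

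**6. The other binary pairs in the paragraph.** The multivariable rows use 270×0.7 = 189 per group, for the 30% of variation explained.

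| Pair | Stated OR | Computed OR | Power |
|---|---|---|---|
| Reinfection, bivariate: 2.5% vs 7.8% | 3.3 | 3.30 | 79.7% |
| Resistance, multivariable: 7% vs 16.2% | 2.5 | 2.57 | 80.0% |
| Reinfection, multivariable: 2.5% vs 9.3% | 4.0 | 4.00 | 80.4% |

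All three pairs agree with their odds ratios and with 80% power under the same method. Only the 1.8 is out of line.

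**7. Resistance by arm (an assumption, not a figure from the plan).** Suppose 65% of SVR failures in each arm develop resistance and SVR in the PN arm is 80%, so PN resistance is 0.65×20% = 13.0%. With 270 per arm:

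| Assumed mDOT SVR | mDOT resistance | OR | Power |
|---|---|---|---|
| 87% | 8.45% | 1.62 | 40% |
| 89% | 7.15% | 1.94 | 62% |
| 90% | 6.50% | 2.15 | 72% |
| 91% | 5.85% | 2.40 | 81% |

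**The case against.** The strongest reply is that little follows from the error. The correct rate pair is printed beside the wrong odds ratio, so a careful reader already has the right effect. The sample size was set by feasibility of recruitment, resistance is a secondary outcome, and no analysis or decision rule uses 1.8. All of this stands. It limits the point to a misstated figure but does not make the figure right.

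A reader might also infer that the protocol promises over 80% power for its secondary objective on resistance by arm (3.2, item iv: "whether the proportion who develop drug resistance is higher in the PN arm compared to mDOT arm"), because arm is a binary variable. The documents do not support that. The sentence belongs to the search for associated factors, where 11.11 brings in the arm indicator for adjustment only, and nowhere is a power given for resistance by arm. Nor can one be read off 11.3, which gives an SVR rate for the PN arm only. The 89% for mDOT in 11.10 is a minimally detectable alternative, and the 65% resistance fraction is not stated by arm. The power in step 7 runs from 40% to 81% as the assumed mDOT SVR goes from 87% to 91%, so no single value should be attributed to the plan.

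Finally, it is tempting to add that uneven factor splits always do worse. They do not: with a 10% overall rate, 40% exposed gives 53.9% against 51.9% at 50:50. More extreme splits do lose power.

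**Conclusion.** The statement is wrong as written. For binary variables in the bivariate resistance analysis, the odds ratio that matches the protocol's own rate pair is 2.23, with about 80% power. The printed 1.8 has about 50%. These figures rest on an even split of 540, a 7% base rate and a two-sided 0.05 test; the conclusion survives the variants in step 5. The error is confined to one number. It overstates sensitivity to binary factors with odds ratios between 1.8 and about 2.2, and leaves the continuous-variable thresholds, the reinfection figures, the sample size and the primary analysis untouched. It is not evidence of a false power claim for resistance by arm.

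**What to change.** In Protocol 11.11 (Power analysis), change the binary, bivariate resistance threshold from 1.8 to an odds ratio of at least 2.2 (7% vs 14.4%), and state that an even split is assumed. The 2.2 is 2.23 rounded, so the rate pair should stay beside it. Leave the continuous-variable odds ratios alone, including the 1.8 that appears later for continuous variables and for adherence. No SAP change is needed.

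Optionally, add a note on resistance by arm, labelled as an assumption and not attributed to 11.3: with PN SVR of 80% and 65% of failures resistant in each arm, power at 270 per arm is about 40%, 62%, 72% and 81% for mDOT SVR of 87%, 89%, 90% and 91%.

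The cost is protocol wording only. Design, data collection and analysis do not change; the stated detectable effect becomes less favourable.
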